1.3 Objectives of the clinical investigation

The proposed clinical investigation is a feasibility study directed toward:

Specific Aim 1: Investigate the safety and efficacy of using NeuroPort Arrays for chronic recording of neural activity from the motor cortex of individuals with upper limb impairments.

- Specific Aim 1a: Document the safety of using the NeuroPort Arrays for chronic recording of neural activity. Monthly neurological and physical examinations will be conducted and documented for the duration of the trial. Any serious adverse events that occur as part of this investigation will be reported in accordance with the FDA’s expedited reporting requirements.
- Specific Aim 1b: Characterize signal quality recorded with the NeuroPort Array during long term implantation in the motor cortex of individuals with tetraplegia. Primary measurements of signal quality include the number of units recorded by the array and the firing rate of single neurons measured during specific tasks (such as imagined hand movement) [6, 45, 46].

Specific Aim 2: Demonstrate that individuals with tetraplegia can learn to successfully control a variety of external devices and computer-driven tasks using signals recorded with two NeuroPort Arrays. We aim to achieve high-dimensional control of complex systems including both a virtual and robotic dexterous hand and arm to perform grasping and reaching tasks which are essential for activities of daily living. This will be measured over the duration of implantation by computing success rate for a given task as well as the amount of computer assist that is required.

Specific Aim 3: Use MEG to localize areas of the brain that can be voluntarily modulated. These results will be compared to pre-surgical mapping results with fMRI and provide additional information for planning the location of electrode implantation.

- Specific Aim 3a: At the optional follow-up MEG visits, we will use the same paradigms to localize areas of the cortex that can be voluntarily modulated to determine if BMI training has induced neuroplasticity. We expect the areas of cortex responsible for voluntary movement will be more strongly activated with more localized responses.

Specific Aim 4: Conduct a sleep study to measure the quantity and quality of sleep each night for a specified period of time to help clarify the role of sleep in motor learning.

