2.4.2 Experimental procedures

Pre-surgical procedures and electrode implantation will occur within 6 months after the subject undergoes screening procedures. We will work with each individual to determine the optimal testing schedule. We will photograph or videotape portions of the experimental sessions. Appropriate UPMC permission will be obtained as needed for any photographs or videotaping of participants. All experimental procedures are described below.

Demographic and Medical History Questionnaire:

The subject will be asked to provide basic demographic information (age, weight, height, etc.) via self-report. We will also ask questions about their medical history including the date of injury or diagnosis and their current level of function. Finally, we will ask questions related to improvement of quality of life and BMI technology. A complete copy of the questionnaire is included with the Case Report Forms in Appendix I. This questionnaire is expected to take less than 30 minutes to complete and can be completed at any of the study visits.

Pre-surgical Magnetoencephalography (MEG) Testing:

Subjects will participate in a MEG scan prior to surgery where they will be asked to perform simple imagined or attempted movements which will provide additional data related to the ideal site for electrode implantation. Similarly, they may be asked to observe actions performed by others. These actions will be simple movements such as hand grasp or tongue movement. As part of the standard protocol for MEG testing, we may attach additional sensors (using tape or an adhesive) to record head position, electroencephalography (EEG), electrocardiography (EKG), electromyography (EMG), or electro-oculography (EOG). EEG is an additional measurement of neural activity. The other recordings allow us to correct for noise sources or head movement. MEG and all of the related recordings are completely non-invasive. The MEG test allows us to measure cortical sources of activity with high spatial and temporal resolution. MEG testing

following the same procedure will be performed again after BMI testing is completed to determine if plasticity has been induced. For example, we would expect the sources responsible for imagined movement to be stronger following BMI training. The pre-surgical MEG session is expected to take less than 2 hours. All MEG scans will take place at the UPMC Brain Mapping Center at UPMC Presbyterian Hospital.

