2.4.3 Follow-up procedures

Post-surgical MEG testing:

We will ask the subject to come back for up to 3 MEG sessions within 6 months after completion of the BMI training. The follow-up MEG sessions are optional

visits for the subjects. If the subject is interested in participating, we will plan to schedule the visits at 2 weeks, 6 weeks, and 3 months after the explantation surgery. The same tasks that were completed during the pre-surgical MEG session will be repeated. In addition to measuring changes in single unit activity over the duration of the study, the MEG studies will allow us to determine if plasticity was induced due to BMI training in terms of volitional modulation of motor cortex activity. These visits are expected to last up to 2 hours each.

Clinical follow-up:

Follow-up visits will be scheduled in order to ensure that the bone flap and Patient Pedestal sites are healing properly. These visits will be scheduled at the discretion of the study neurosurgeon and the subject. We expect that each subject will have two follow-up visits with the study neurosurgeon and their clinical team at 1 and 4 weeks (+/- 3 days) after explantation. Depending on the healing process of the implantation site and percutaneous port, additional imaging studies (x-ray, CT scan, or MRI) may be performed although this is unlikely.

Post-explant counseling:

Subjects will be scheduled for an appointment with a licensed rehabilitation psychologist to assure that they have an opportunity to discuss any concerns they may have post explantation.

2.4.4 Study compliance and withdrawal:

The subject will be under medical supervision for the duration of this study. Their health will be the top priority and participation will be discontinued if surgical intervention is required. The study neurosurgeon and PI will be primarily responsible for evaluating the subject's condition. Complications that could result in removal from the study (and having the NeuroPort Array removed) include:

- Treatment resistant (serious) infection at the implantation site or Patient pedestal
- Array technical malfunction resulting in an inability to collect data that is useful for brain-control tasks
- Serious medical complications that compromise the subject's safety or health

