Specific Aim 3: Source localization (combining the MEG and structural MRI data) will be used to identify the anatomical foci of cortical activation controlling imagined and/or attempted movement. The coordinates (x,y,z) of the center of activation can be computed with fMRI or MEG relative to the head coordinate system defined using bony landmarks. The location and area of cortical activation measured by fMRI and MEG during imagined and/or attempted movement will be compared for each subject. A paired t-test will be used to compare location and area of cortical activation measured by the two imaging techniques using data from all participants, although the power of this test may be limited by sample size. Qualitative comparisons will be informative and we expect agreement between the two imaging techniques in terms of localizing the area for array implantation. MEG

potentially offers additional information due to higher temporal resolution.

Specific Aim 3a: Cortical modulation will be calculated as the power of the 4-40 Hz frequency band of MEG data that is recorded during imagined and/or attempted movement. Specific Aim 3a will be evaluated by applying repeated measures ANOVA to test for differences in modulation (magnitude and total area) during imagined and/or attempted movement during the pre-surgical procedures and the follow-up sessions.

The study will be considered a success if the device is not explanted for safety reasons during the 12-month post-implant evaluation. Further participants should demonstrate successful control of a high degree of freedom assistive technology in order to safely perform a task that replicates normal activities of daily living, such as grasping a cup with a robotic manipulator. This study is not being proposed to support marketing applications (510(k) or PMA) for the NeuroPort Arrays. Instead, the goal is to demonstrate that three-dimensional microelectrode arrays provide a safe way to record sufficient neural information for controlling complex assistive devices that will increase the independence of individuals with disabilities.

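### Aim 3a measures cortical modulation as MEG power during the task with no rest reference, so a between-session shift in background power or gain passes straight into the outcome

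*Combined protocol and SAP*

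**What the plan says.** Section 2.5.3 defines the Aim 3a outcome: "Cortical modulation will be calculated as the power of the 4-40 Hz frequency band of MEG data that is recorded during imagined" or attempted movement. Section 3.5.3 repeats the definition for the extension study. The analysis in both consists of "applying repeated measures ANOVA to test for differences in modulation (magnitude and total area) during imagined and/or attempted movement", comparing the pre-surgical procedures with the follow-up sessions.

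The purpose is given in section 2.4.3: the follow-up scans are to "determine if plasticity was induced due to BMI training in terms of volitional modulation of motor cortex activity". The expected result has a direction. Section 1.3 states "We expect the areas of cortex responsible for voluntary movement will be more strongly activated with more localized responses", and section 2.4.2 states "we would expect the sources responsible for imagined movement to be stronger following BMI training".

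On what is recorded, section 2.4.2 says of the pre-surgical scan that "they will be asked to perform simple imagined or attempted movements which will provide additional data"; subjects may also observe actions performed by others. Section 2.4.3 says "The same tasks that were completed during the pre-surgical MEG session will be repeated", with visits planned at 2 weeks, 6 weeks and 3 months after explantation. Neither section describes a rest condition. The one signal correction described is in section 2.4.2, on the optional additional sensors: "The other recordings allow us to correct for noise sources or head movement".

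**The concern.** Volitional modulation is a change that the subject produces at will, so it has to be measured against something, normally the same subject at rest in the same session. The stated rule has no such term. It takes power during the task and compares it with power during the task at another visit. Whatever alters background power or recording gain between those visits is then counted as modulation.

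The contrast being tested is open to this. The pre-surgical scan comes before both craniotomies, and every planned follow-up scan comes after explantation, about 1 year after implantation in the core study and up to 5 years in the extension. Section 2.4.2 allows titanium plates to secure the bone flap, and the same section lists metal in the head or neck among the reasons that MEG may be contraindicated. Repeated measures remove stable differences between subjects; they do not remove a change that occurs between the first scan and the later ones.

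The plan also fixes no sign. The hypothesis is that activation becomes stronger, but the ANOVA is non-directional and nothing says whether stronger means more or less power in the 4-40 Hz band. At stake is whether Aim 3a can be interpreted at all as evidence of training-induced plasticity.

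**Working it through.** The plan gives no effect size, variance, significance level or power for Aim 3a, so there is no figure to reproduce. The check has two parts: a search of the text for a reference condition, and the algebra of the stated outcome.

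**Text.** Sections 1.3, 2.4.2, 2.4.3, 2.5.3, 3.4.3 and 3.5.3 were read for a rest or pre-cue reference, a normalisation, a sign convention, or a threshold for total area. None is stated. The word baseline is used for a visit column in Table 1 and for computer-assist levels under Aim 2, not for MEG.

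**Identity.** Let R be in-band rest power times session gain, m the fractional change from rest to task (the modulation), and T the task power (the plan's outcome). Then

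T = R × (1 + m), so T2/T1 = (R2/R1) × (1 + m2)/(1 + m1).

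The aim concerns m. The outcome is T. All values of m and R below are assumed.

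1. *Masking and reversal, task raises power.* Let m grow from 0.2 to 0.3.
   - With R constant, T2/T1 = 1.3/1.2 = 1.083, a rise of 8.3%.
   - T falls if R2/R1 is below 1.2/1.3 = 0.923, that is, if R falls by more than 7.7%.
   - With R down 10%, T2/T1 = 0.9 × 1.083 = 0.975, although modulation has grown.
2. *The same, task lowers power.* Let m go from -0.2 to -0.3.
   - With R constant, T2/T1 = 0.7/0.8 = 0.875, a fall of 12.5%.
   - T rises if R rises by more than 0.8/0.7 - 1 = 14.3%.
3. *Mimicry.* With m unchanged, T2/T1 = R2/R1. A 10% or 20% change in R appears as a 10% or 20% change in the outcome.
4. *Direction.* Suppose a share w of in-band rest power is lowered by the fraction |m| and the remainder raised by |m|, with R constant and |m| doubling from 0.2 to 0.4. T changes by +16.7%, +9.1%, 0.0%, -11.1% and -25.0% for w = 0, 25, 50, 75 and 100%. The same gain in modulation can give a rise, no change or a fall.
5. *With a reference.* T/R = 1 + m in each session, so R cancels. In step 1, T/R goes from 1.2 to 1.3 whatever R does.
6. *Effect on the test.* The simulation used 5 subjects, 4 sessions (one before surgery, three follow-ups), repeated measures ANOVA on log power at an assumed 0.05 level, and 10,000 runs. Modulation was unchanged, with mean m = -0.30 and SD 0.05; the within-subject SD of log power was 0.1. A rest-power shift common to all subjects was applied after the first session.

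| Common shift in rest power | Rejection, task power | Rejection, task/rest ratio |
|---|---|---|
| 0% | 5.1% | 4.7% |
| 10% | 16.1% | 5.2% |
| 20% | 50.8% | 5.4% |
| 30% | 84.8% | 5.1% |

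   If instead the shift varies at random between subjects with no common component (log SD 0.1 to 0.3), rejection on task power stays below 9% when each subject's shift persists across follow-ups, and close to 5% when it varies by session.

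**The case against.** The strongest reply is that this is an omission, not a choice. The plan says power; it does not say raw or absolute power. It calls the outcome modulation and gives it a total area, which needs some threshold or contrast. The Aim 3 text just before it concerns source-localised activation. A task-versus-rest contrast may well be intended. That is possible, but the rule as written says how the number is calculated and has no reference term. An analyst who followed it would compute task power.

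Second, section 2.4.2 allows correction for noise sources and head movement. This stands in part: head position should not be used as the main example of a session effect. The sensors are optional, however, and the correction does not deal with arousal, background power or changes after surgery.

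Third, every magnitude above is assumed, and large false-positive inflation needs a shift shared by the subjects. This stands. The documents do not show that such a shift occurs; two craniotomies between the compared scans make it possible.

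A reader might go further and infer that the measure is bound to move against the hypothesis, because imagined movement lowers power in part of the band. The documents do not support that. They do not say whether the tasks raise or lower 4-40 Hz power, and they do not equate stronger activation with more power. Reversal is a possibility under stated conditions, not a prediction.

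Finally, the impact is limited. Section 2.4.2 says that plasticity measured by MEG is not the main priority and that similar measures can come from neural data recorded during training. Follow-up MEG is optional, and at most 5 subjects are implanted.

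**Conclusion.** The concern holds in this form: as written, the Aim 3a outcome mixes background power and session gain with the volitional modulation it is meant to measure, and the sign of a result has no agreed meaning. The identity holds for any values. The illustrative figures, such as the 7.7% break-even, depend on assumed modulation, and the rejection rates depend also on assumed variances and on a common shift. The true size of the problem cannot be obtained from the documents.

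This is more than a missing detail, because a stated rule is in place and a same-session ratio is a better and inexpensive alternative. It should be changed, but it affects only Aim 3a. The safety success criterion and the device-control criterion do not use this outcome.

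**What to change.** In sections 2.5.3 and 3.5.3, define modulation as task power relative to rest or pre-cue power in the same session, for example the log ratio. Define total area on the same task-versus-rest contrast, with its threshold. State in advance which direction of change counts as stronger activation. Reporting by sub-band is optional.

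In section 2.4.2, state that a rest or pre-cue interval is recorded at the pre-surgical scan; sections 2.4.3 and 3.4.3 then carry it forward, because they repeat the same tasks.

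The ratio removes multiplicative shifts only. Noise power N added equally to rest and task would shrink the measured modulation from m to m × R/(R + N), so the noise correction in section 2.4.2 is still needed.

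The cost is analysis wording if the recordings already hold rest or pre-cue intervals, which the protocol does not say. Otherwise it is a few minutes of rest recording within MEG visits already planned at up to 2 hours. The interval has to be in place before each subject's pre-surgical scan, because that scan cannot be repeated once the arrays have been implanted.

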2.3.2 Anticipated number of research subjects

A maximum of 10 participants will be enrolled in order to implant a maximum of 5 subjects. It is anticipated that we will implant no more than 1 subject every 6 months. Recruitment rates will be monitored by our DSMB. Because it is possible that a subject may enroll and then be determined to be ineligible for anesthesia and/or surgery, the maximum number of subjects enrolled may exceed the number implanted. Subjects will be enrolled as necessary to maintain the target number of subjects implanted. Recruitment will not begin until we have received IRB approval.

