2.5 Study outcome evaluations

2.5.1 Study endpoints

The NeuroPort Arrays will be removed 1 year (+/- 30 days) after implantation. A participant will be considered a success for safety if the device is not explanted for safety reasons during the 12-month post-implant evaluation. If the subject experiences treatment resistant (serious) adverse events, he or she will be withdrawn and the arrays will be explanted early (See Section E 2.4.4). The study may also end early if the subject is non-compliant (See Section E 2.4.4).

We believe it is possible that a participant will not want the array removed. If the participant wants the NeuroPort Arrays to stay in, the study PI and neurosurgeon will assess whether this is acceptable. This decision will be based on whether or not the participant is at increased risk by leaving the arrays in and whether the device is still measuring neural activity that is sufficient for brain control. We will consult our DSMB if conflicts arise. One participant in the BrainGate trial has had a NeuroPort Array implanted for more than 1000 days without adverse event [9]. If the NeuroPort Arrays remain implanted for more than 1 year, we will continue to perform clinical follow-up as described in the current protocol. We may also continue brain-machine interface testing although the frequency of the training sessions may be reduced. We will remove the NeuroPort Arrays at anytime as directed by the participant, or as dictated by their clinical condition.

If the participant wishes to leave the NeuroPort Array implanted, but the study PI and neurosurgeon do not feel that it is in their best interest, the participant will be counseled that they should have the NeuroPort Array removed and that not doing so could result in clinically significant adverse events. They will also be informed that brain-machine interface training will not continue. The consent form includes a statement that participants will be financially liable for any medical care resulting from complications of not having the device removed upon instruction of the study PI. We will however allow participants to have the device removed at anytime and the explantation costs would be covered by this study.

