2.5.2 Sample size determination

A maximum of 10 participants will be enrolled in order to implant a maximum of 5

subjects. Because it is possible that a subject may enroll and then be determined to be ineligible for anesthesia and/or surgery, the maximum number of subjects enrolled may exceed the number implanted.

New information will be learned with each participant, as this is a feasibility study. Single-subject design statistical analyses will be used. Our main goal is to demonstrate the safety and efficacy of NeuroPort Arrays for long-term recording of neural activity in order to control a high-dimensional BMI.

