2.5.3 Outcome data and data analysis

Specific Aim 1a will be fulfilled through monthly clinical examinations as well as observations made by the research staff, participant, or their caregiver throughout the trial. Research staff will document volunteered and observed adverse events at least weekly during the BMI training sessions. Adverse events will be documented and reported to University of Pittsburgh IRB and to the FDA in accordance with the respective reporting requirements and in the annual report. This documentation will serve as documentation of the safety of device in this small sample.

Specific Aim 1b is to characterize signal quality (firing rate, number of units recorded) over the duration of implantation. Data to support this aim will be collected at least weekly during the BMI training sessions. Our primary method of analysis will be to plot the trends in signal quality measures over time. The trend will be quantified using regression techniques.

Specific Aim 2 is to demonstrate that individuals with tetraplegia can learn to successfully control of a variety of external devices and computer-driven tasks using signals recorded with the NeuroPort Array. In addition to video documentation of brain-controlled device operation, we will quantify the number of degrees of freedom achieved by each participant at regular intervals for the duration of implantation. Multiple baselines will be defined as the level of computer assist will decrease with training. We will use regression to quantify changes in performance at a given assist level. Similarly, trends in success rate and computer assist level for a given task will be quantified over the duration of the trial using regression.

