Specific Aim 3: Source localization (combining the MEG and structural MRI data) will be used to identify the anatomical foci of cortical activation controlling imagined and/or attempted movement. The coordinates (x,y,z) of the center of activation can be computed with fMRI or MEG relative to the head coordinate system defined using bony landmarks. The location and area of cortical activation measured by fMRI and MEG during imagined and/or attempted movement will be compared for each subject. A paired t-test will be used to compare location and area of cortical activation measured by the two imaging techniques using data from all participants, although the power of this test may be limited by sample size. Qualitative comparisons will be informative and we expect agreement between the two imaging techniques in terms of localizing the area for array implantation. MEG potentially offers additional information due to higher temporal resolution.

Specific Aim 3a: Cortical modulation will be calculated as the power of the 4-40 Hz frequency band of MEG data that is recorded during imagined and/or attempted movement. Specific Aim 3a will be evaluated by applying repeated measures ANOVA to test for differences in modulation (magnitude and total area) during imagined and/or attempted movement during the pre-surgical procedures and the follow-up sessions.

Specific Aim 4: Sleep quality measures will be correlated to BMI performance on the following day while controlling for differences in task difficulty. Linear regression will be used to determine the most predictive sleep quality metrics.

The study will be considered a success if the device is not explanted for safety reasons during the 12-month to 5 year post-implant evaluation. This study is not being proposed to support marketing applications (510(k) or PMA) for the NeuroPort Arrays. Instead, the goal is to demonstrate that three-dimensional microelectrode arrays provide a safe way to record sufficient neural information for controlling complex assistive devices that will increase the independence of individuals with disabilities.

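### The study-level safety success rule has no denominator or precision, and a design with at most five implanted participants cannot demonstrate safety

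*Combined protocol and SAP*

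**What the plan says.** Section 2.5.1 defines safety success for one person: "A participant will be considered a success for safety if the device is not explanted for safety reasons during the 12-month post-implant evaluation". Section 2.5.3 then applies almost the same sentence to the whole study: "The study will be considered a success if the device is not explanted for safety reasons during the 12-month post-implant evaluation". Sections 3.5.1 and 3.5.3 repeat this step for the extension, the latter with "The study will be considered a success if the device is not explanted for safety reasons during the 12-month to 5 year post-implant evaluation". No section says how many participants must succeed for the study to succeed, how small the number implanted may be, or what estimate or interval will accompany the result.

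The sample size is a ceiling. Section 2.5.2 states "A maximum of 10 participants will be enrolled in order to implant a maximum of 5", and 2.3.2 agrees. The extension takes up to 5, all from the core study (3.3.2, 3.5.2). No event rate or precision target lies behind these numbers.

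The stated purpose is stronger than the design: "Our main goal is to demonstrate the safety and efficacy of NeuroPort Arrays for long-term recording of neural activity" (2.5.2). The closing paragraphs of 2.5.3 and 3.5.3 use the same verb about the arrays being safe.

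Other text is more cautious. The trial is called a feasibility study (2.2.1, 2.5.2, 3.5.2). Section 2.5.2 adds "Single-subject design statistical analyses will be used". Under Aim 1a, 2.5.3 says of the adverse-event record: "This documentation will serve as documentation of the safety of device in this small sample". Both 2.5.3 and 3.5.3 say that the study is not meant to support a marketing application. Section 2.5.3 also expects participants to show functional control of an assistive device; 3.5.3 has no such sentence.

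**The concern.** A per-participant outcome has become a study verdict without a rule for combining participants. If one of five arrays were removed for safety, one reader could report failure (not all were retained) and another success (most were). The text does not settle it.

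The second problem is what the verdict would mean. The plan pairs a pass/fail sentence with a goal of demonstrating safety, but attaches no measure of uncertainty. A reader of the final report could take success as evidence that the risk of a safety explant is low, when data from five people or fewer are compatible with a very high risk. On the most natural reading, falling short on recruitment would also make success more likely, which is the wrong direction for a safety criterion.

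**Working it through.** **Inputs.** At most 5 implanted, with no minimum (2.3.2, 2.5.2). The endpoint is a safety explant within 12 months, yes or no, per participant (2.5.1). The documents give no expected safety-explant risk, confidence level or threshold. I use 95% exact (Clopper-Pearson) limits. Where a true risk *r* is needed, I show a range, as an assumption of mine.

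**The plan's own figure.** The maximum of 5 has no formula or inputs, so there is nothing to reproduce.

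**Step 1: what zero events can show.** For 0 events in *n*, the upper limit is 1 − 0.025^(1/n) two-sided and 1 − 0.05^(1/n) one-sided.

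| n implanted | Two-sided 95% | One-sided 95% |
|---|---|---|
| 1 | 97.5% | 95.0% |
| 3 | 1 − 0.025^(1/3) = 70.8% | 1 − 0.05^(1/3) = 63.2% |
| 4 | 60.2% | 52.7% |
| 5 | 1 − 0.025^(1/5) = 52.2% | 1 − 0.05^(1/5) = 45.1% |

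The best possible result, 0 of 5, does not exclude a true risk of one in two. With 1 of 5 the two-sided interval runs from 0.5% to 72%.

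**Step 2: how the rule behaves if it means zero safety explants among those implanted.** The chance of meeting it is (1 − r)^n.

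| Assumed r | n = 1 | n = 3 | n = 5 |
|---|---|---|---|
| 20% | 80% | 51% | 33% |
| 30% | 70% | 34% | 17% |
| 50% | 50% | 12.5% | 3.1% |

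The chance falls as *n* rises, so fewer implants make success easier. The reading matters: if one explant in five were tolerated, the chance at r = 30% would be 0.7^5 + 5 × 0.3 × 0.7^4 = 0.168 + 0.360 = 53%, against 17%.

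**Step 3: is fewer than five realistic?** Section 2.3.2 anticipates no more than one implant every 6 months, and 1.4 expects the study to last 3 years. Implants at months 0, 6, 12, 18 and 24 put the fifth 12-month evaluation at 24 + 12 = 36 months. Five fit only with no slack for screening.

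**Step 4: the extension.** Entry requires good outcomes at 6 months or later, no unresolved significant adverse events and at least 4-dimensional control (3.3.1, 3.3.3). Someone explanted for safety in the core study cannot enter. For illustration, suppose 1 of 5 is explanted in the core study and the other 4 enter without a later event. The extension alone shows 0 of 4 (upper limit 60.2%); among all implanted it is 1 of 5 (0.5% to 72%). Participants may extend by 6 months to 4 years (3.3.3), so the same success label can rest on very different follow-up.

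**The case against.** The strongest defence is that this is a small descriptive feasibility study. No test, significance level or regulatory decision depends on the success sentence, and five participants need not be powered. That sentence says when the study counts as a success, not that safety is then proven. Aim 1a in 1.3 is to document safety, and 2.5.3 acknowledges a small sample. Explant status is not the only safety evidence: adverse events are recorded at least weekly, and an independent board reviews risk and accrual.

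Much of this stands. It keeps the severity moderate and rules out asking for more participants. It does not supply the missing denominator or interval. The small-sample remark concerns adverse-event documentation, and the only caution about power in 2.5.3 concerns the imaging comparison. Board oversight during conduct does not define the final claim.

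A reader might infer more, in three ways that the documents do not support:

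- *One uneventful participant makes the core study a success.* Section 2.5.3 also expects functional control, so the safety sentence is not the whole criterion. That expectation still gives the safety claim no denominator, and 3.5.3 lacks it, although extension entry requires prior control.
- *The rule has a known chance of false success.* The figures in Step 2 depend on the zero-explant reading and on assumed risks. The documents fix neither.
- *The limits should be judged against the infection figures in 4.1.* Infection is not a safety explant. Sections 2.4.4 and 4.1 link removal to infection that resists treatment, and there are other causes of removal. No required sample size follows from those figures.

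**Conclusion.** The point holds, at moderate severity. The study-level safety sentences in 2.5.3 and 3.5.3 have no denominator and no precision, and demonstrating safety is beyond a design with at most five implanted. Even the best result leaves a two-sided upper limit of 52% (45% one-sided); with three implanted it is 71% (63% one-sided).

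These limits do not depend on how the rule is read. They assume independent participants with a common risk, each followed for the full 12 months; early removal for other reasons would leave less information. The tendency for success to become easier with fewer implants (70% at n = 1 against 17% at n = 5, for an assumed 30% risk) is conditional on the zero-explant reading and is illustrative only.

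**What to change.** 1. In 2.5.3 and 3.5.3, replace the study-level safety pass/fail sentences with a reporting rule: safety explants as x of n over all implanted participants, with the two-sided exact (Clopper-Pearson) 95% interval. Use that one interval throughout. Once the result is an estimate, no pass threshold is needed.
2. For the extension, report x of n against everyone implanted in the core study as well as against those who entered, and give follow-up in implant-years.
3. In 2.5.2 and the closing paragraphs of 2.5.3 and 3.5.3, restate the safety goal as estimating safety or providing preliminary evidence on it.
4. State in 2.5.2 that 0 of 5 leaves a two-sided 95% upper limit of 52%.

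The cost is a few sentences in three sections. No one extra is enrolled and no new data are collected. The downside is that the stated safety claim becomes less favourable.
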